### 1. Introduction

This document details our analysis plan for: Fresh Food Farmacy: A Randomized Controlled Trial. This will serve as a record of the planned analyses to avoid concerns over searching for results *ex post*. We anticipate that further analyses will be conducted as more outcome data become available, and as new ideas are inspired by the initial findings. It is also possible that our planned analyses may be modified based on what we learn during the initial launch phase. Any such additions will be noted in a later version of this plan with an indication of the date on which they were added.

The outline of this plan is as follows: Section 2 briefly describes the intervention and trial details. Section 3 describes the data and the outcomes of interest; Section 4 presents the main empirical models, including planned analysis for heterogeneous effects; and Section 5 concludes with caveats and interpretation issues.

### 2. The intervention

In July 2016, Geisinger began piloting the Fresh Food Farmacy (FFF) program for food-insecure patients with diabetes in Shamokin, PA. Fresh Food Farmacy brings a "food-as-medicine" approach to treat these patients. Participants receive a referral to the Fresh Food Farmacy dietitian who provides a prescription for fresh food for the patient and everyone else in their household, enough for 2 meals per day, 5 days per week. (They do not provide 3 meals per day, 7 days per week because it is assumed that the households have other sources of meals, and the program wishes to minimize waste.) The program lasts indefinitely; there is no predetermined end date.

FFF participants receive education on how to use the food. This includes dietitian consultations, new recipes each week, and cooking classes. Next, the program expects, but does not compel, participants to attend diabetes self-management classes from a prominent program developed at Stanford University. Clinic staff include nurses who check whether

patients have received preventive care, such as eye and foot exams and influenza vaccination. Participants' biometric measures (HbA1c, fasting glucose, weight, BMI, blood pressure, total cholesterol, LDL cholesterol, and triglycerides) and medication usage are tracked on a regular basis. On a case-by-case basis, participants may receive cooking equipment to help in food preparation.

FFF has received considerable attention (e.g. Aubrey, 2017; Davidson 2017; Feinberg et al., 2017 and 2018), as it uses a holistic approach to address a key Social Determinant of Health (food insecurity), and because providers, public health officials, and payers are increasingly willing to consider such innovative approaches to improve the health of patients. Indeed, over 100 healthcare systems have consulted with Geisinger about their operation and are considering adopting it. Geisinger recognizes that a key next step is to allow for a randomized-controlled trial in order to accurately measure the effectiveness of the FFF program.

Geisinger Health piloted the FFF in Shamokin, PA, and plans to expand the program in the coming months, first in Scranton, PA and then in Lewistown, PA. The program faces capacity constraints such that the program cannot be offered to all eligible participants on the first day. We will carry out a pragmatic randomized controlled trial; eligible patients who are randomized to the treatment group will begin the FFF program immediately, while those randomized to the control group will begin the FFF program 6 months later. This will allow a rigorous examination of the effects of the program for outcomes 6 months after randomization (when the treatment group has been in the FFF program for 6 months and the control group has not yet started the FFF program).

# **Enrollment & Randomization**

Enrollment in the trial will be conducted by Geisinger in a process similar to the one currently used to enroll patients into FFF.

Patients must satisfy the criteria based on the records at the time of recruitment noted in the IRB protocol. In particular, they must be adults with Type II Diabetes and an HbA1c  $\geq$  8.0 (as determined in Geisinger Health EMR data), food insecure (as determined from a two-question

survey instrument), and whose residence is within 25 miles or 45 minute drive from the FFF clinic (a distance that could change in the future), as measured by the patient's ZIP code centroid.

Geisinger Health patients who are *potentially* eligible will be randomized to determine the order in which they are recruited. (To clarify, this is not the randomization for assignment into the treatment and control groups, it is a randomization to determine the order in which potentially eligible patients are contacted and then later randomized to the treatment and control groups.) Depending on the speed of recruitment, we will consider comparing patients enrolled earlier vs. later to consider the evolution of A1c over a longer time horizon than 6 months (e.g. someone recruited 3 months into the trial and assigned to control will have HbA1c measured at 6+3=9 months after "potential enrollment").

Recruitment will be conducted over the phone; the program will be described, consent will be sought, and then patients will be randomized to either treatment ("start FFF now") or control ("start FFF later"). Note that all patients eligible for FFF, whether or not they agree to participate in the study, will be randomized to determine the timing with which they will enroll in FFF. This is the way the program is being introduced, akin to a lottery, and ensures that there is no incentive to refuse to participate in the study in order to start FFF sooner. Recruitment staff will discover whether the patient is randomized to start now or start later in a tamper proof REDCap application, which consults a randomized allocation table that the recruiter cannot access and a treatment status that is locked along with the patient's identifying information and study ID. The recruiter will then set up the patient's first appointment for those in the treatment group and will reach out to patients 5 months later to set up appointments for the group randomized to start later. We anticipate finding the patients 5 months later because all subjects are Geisinger Health patients, whose current address is on file, and we will ask for two other contacts at the time of recruitment.

The randomization is stratified using levels of HbA1c: <8.0 (in the event that the threshold is lowered),  $\geq$ 8.0 and <9.5, and  $\geq$  9.5 to attempt to ensure balance on a key pre-study control and because we are interested in estimating effects separately by these categories to inform

threshold setting in future applications. The randomization happens separately by location (Scranton and Lewistown) as well.

The trial will launch in April 2019 in Scranton, and likely June 2019 in Lewistown. We plan to continue enrollment until we attain at least 500 subjects (half in treatment) or when the recruitment period has lasted 2 years. If recruitment slows, we will consider lowering the eligibility threshold to an HbA1c of at least 7.5 rather than 8.0, and we may consider expanding the geographic limit.

### 3. Data sources and outcomes

### 3.1. Data sources

There are three main sources of data:

A. Geisinger Health Electronic Health records. These include clinical outcomes that are collected as part of the study. Subjects go to a Geisinger lab for a blood test at no cost (more on potential attrition is discussed below); the blood is tested for HbA1c, fasting glucose, total cholesterol, LDL cholesterol, and triglycerides. Weight, BMI and blood pressure are also recorded. The records also include inpatient, outpatient, and ED encounters, and scheduling information. All subjects are Geisinger Health patients. Utilization is largely at Geisinger facilities, although inpatient stays at other hospitals may be visible in the EHR record.

- B. Fresh Food Farmacy operational data. This includes encounter data at FFF, including number of weeks in which the patient picked up food, their choices of food, dietitian appointments, and classes. Program participants are surveyed upon entry into FFF, and again at 6 months and at 12 months, and the surveys have been modified to measure outcomes of interest. This will allow us to ask questions about diet, healthy behaviors, self-efficacy, and self-assessed health.
- C. Geisinger Health Plan data. For subjects who receive their insurance from the Geisinger Health Plan, expected to be more than half of the subjects, paid claims are available. This

allows us to measure utilization at providers other than Geisinger Health, albeit on a smaller and selected sample. Highmark (another local insurer) may share utilization data for their patients that are participating in the program as well.

## 3.2. Primary outcome

The primary outcome we will analyze is the subject's HbA1c at 6 months into the trial. This is a standard biomarker for diabetes that is influenced by diet and medication adherence. It is a measure of whether the program is improving health; and it is strongly associated with healthcare utilization (e.g. Oglesby et al., 2006, Juarez et al., 2013).

## 3.3. Secondary outcomes

### *6-month outcomes*

Secondary outcomes of interest include other biomarkers at 6 months: fasting glucose, weight, BMI, blood pressure, total cholesterol, LDL cholesterol, and triglycerides.

We will also examine outcomes based on self-reported survey data, including diet, exercise, and other healthy behaviors, self-efficacy, self-assessed physical and mental health, and patient satisfaction with Geisinger Health as a whole. We will also measure whether the patients have improved their understanding of diabetes and healthy eating.

Other outcomes help us understand the nature of the services offered. The control group has access to dietitian consultations and diabetes self-management classes as part of the standard of care, but we believe the take-up of such services will be higher among the treatment group. We ask about these consultations and classes in the patient surveys to verify that this is the case. We also survey participants about adherence to diabetes best preventive care and whether the subjects are signed up for SNAP benefits, as the program encourages take-up.

Using encounter data, we will also document the level of engagement with the program at the FFF clinic, including the number of weeks that the participants picked up food, the number of dietitian encounters, and the number of classes taken.

Health care utilization is another important secondary outcome. We will examine, at six months, the difference between the treatment and control group in: probability of any inpatient stay, any ED visit, any hospital visit (inpatient or ED). We will also examine the number of such visits, as well as the number of outpatient visits outside the FFF program. We will also examine medication usage, including insulin. Related, we will test for differences in paid claims both in those categories and in the amount paid among the Geisinger Health Plan beneficiaries and check that treatment and control are balanced on inclusion in this sample. We expect there may be outliers in payments, so we will estimate models in levels, logs, and check for differences in the distribution including the median. Any effect of the program on such outcomes may take time to materialize and thus may not be visible at 6 months.

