5.3 Specific Aim 2: Measure Effectiveness of FFF on healthcare utilization

Our second specific aim is to evaluate the effectiveness of FFF on healthcare utilization including ED visits and a combination of ED visits and inpatient admissions, as well as costs to Geisinger Health Plan. Direct utilization as part of the program will be considered as a

comparison to reductions in utilization after enrolling in the program. We plan to study program participants as well as their family members who are expected to benefit from the healthy food.

[figure not shown]
We will collect this information from administrative data from electronic health records and Geisinger Health Plan claims. These are additional health outcome measures and provide a way to consider the cost effectiveness of the program. Program data on the use of services by participants will be included for the full comparison of utilization. Our cooperation with Geisinger, which not only conducts the FFF program but also maintains records of medical care utilization, is a strength of this proposal. FFF also provides services for patients who are not Geisinger Health Plan members. Highmark (another local insurer) may share utilization data for their patients that are participating in the program in the future. As with Geisinger data, any Highmark data would be shared with MIT researchers under a DUA that would be submitted to the IRB under an amendment.

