### 12-month outcomes

We will examine the same outcomes at 12 months as we did at 6 months. In doing so, we will be comparing the treatment group (which will have had 12 months of exposure to the FFF program) to the control group (which will have had 6 months exposure to the FFF program). This will be informative about whether the rate of expected improvement in outcomes slows over time.

Health care utilization will also be examined at 12 months. As mentioned earlier, we expect that any effect of FFF on utilization may be visible only with a lag. We have statistical power for the more common 12-month outcomes: any inpatient stay, any ED visit, and any hospital visit (inpatient or ED). We will also examine the number of such visits, as well as the number of outpatient visits outside the Fresh Food Farmacy.

To allow time for the program to affect outcomes, we will also consider outcomes within other timeframes: 90-365 days and 90-180 days.

The program re-assesses food insecurity after one year, so food insecurity will be asked at 12 months; given the nature of the program we hypothesize that the FFF program should considerably reduce food insecurity.

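### The SAP counts outpatient visits only outside FFF, so dietitian and class contacts are counted by who delivers them; counts that follow one rule in both arms should be added

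*SAP*

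**What the plan says.** **Outcome.** Under 6-month outcomes, SAP 3.3 lists inpatient and ED measures "as well as the number of outpatient visits outside the FFF program". The 12-month list uses the same exclusion: "as well as the number of outpatient visits outside the Fresh Food Farmacy". That subsection also adds outcome windows of 90-180 and 90-365 days.

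**Overlap in services.** SAP 3.3 states: "The control group has access to dietitian consultations and diabetes self-management classes as part of the standard of care". It continues: "we believe the take-up of such services will be higher among the treatment group". The treatment arm's contacts of this type sit in the FFF operational data. SAP 3.1 B describes that source: "This includes encounter data at FFF, including number of weeks in which the patient picked up food, their choices of food, dietitian appointments, and classes". SAP 3.3 reports FFF dietitian encounters and classes as engagement measures and does not add them to the outpatient count.

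**Paid claims.** For Geisinger Health Plan members the SAP says: "Related, we will test for differences in paid claims both in those categories and in the amount paid". It does not say whether FFF services generate claims.

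**Protocol.** Section 5.3 says that use within the program will be weighed against reductions elsewhere, and adds: "Program data on the use of services by participants will be included for the full comparison of utilization". Section 8.6 lists outpatient visits among the utilization endpoints with no FFF exclusion.

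**The concern.** A dietitian visit or self-management class can occur in either arm. In a control before FFF entry it happens in usual care and is eligible for the count. In a treatment subject who gets it at FFF it is left out. The rule depends on the deliverer, and randomization changes the deliverer. Substitution alone therefore pushes the treatment count down, even if each person has the same number of contacts.

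At stake is how the outpatient result is read. Protocol 5.3 uses utilization to consider cost effectiveness. A lower outside-FFF count could be reported as less outpatient care when some of that care had only moved. SAP Section 1 presents the SAP as the record of planned analyses, and that record does not contain the comparison that Protocol 5.3 promises.

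**Working it through.** **Is there a figure to reproduce?** No. Table 2 in the SAP covers HbA1c, weight and hospital visits (inpatient or ED). It has no mean, SD or target effect for outpatient visits. As a check on the method only, take the nearest row, hospital visit 0-180 days, with mean 0.39, SD 0.49, √(1−R²) 0.85 and a 30% effect:

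N = 4 × [0.49 × 0.85 × (1.960 + 0.842) / (0.39 × 0.30)]² = 397.9, against 397 stated.

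**The two arms side by side, months 0-6**

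| Contact | Control | Treatment |
|---|---|---|
| Dietitian or class, usual care | counted, if recorded as an outpatient encounter | counted, if recorded as an outpatient encounter |
| Dietitian or class at FFF | none, not yet in FFF | not counted |
| Other outpatient visit | counted | counted |

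**Size of the counting effect.** Let d be the mean number of usual-care dietitian and class contacts per control that are recorded as outpatient encounters. Let s be the share of these that move into FFF in the treatment arm. With total care unchanged:

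difference in the SAP count = −(d × s).

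On an assumed control mean of 5 visits in 6 months, shifts (d × s) of 0.25, 0.5 and 1.0 give 0.25/5 = 5%, 0.5/5 = 10% and 1.0/5 = 20%.

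**How the alternative counts behave.** Assume 5 visits in total per person in each arm, 0.5 of them dietitian or class contacts, all moved into FFF in the treatment arm (s = 1):

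| Count | Control | Treatment | Difference |
|---|---|---|---|
| Outside FFF (SAP) | 5.0 | 4.5 | −0.5 |
| (a) Excluding dietitian and class contacts, both arms | 4.5 | 4.5 | 0 |
| (b) All sources | 5.0 | 5.0 | 0 |

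**Chance of a significant result when total care is the same.** Use 250 per arm, two-sided alpha 0.05, SE = SD × √(2/250) and z = (d × s)/SE. The probability is Φ(z − 1.96) + Φ(−z − 1.96). For a shift of 0.5 and SD 4: SE = 0.358, z = 1.40, probability 28.7%.

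| Shift (visits) | SD 2 | SD 4 | SD 6 |
|---|---|---|---|
| 0.1 | 8.6% | 5.9% | 5.4% |
| 0.25 | 28.7% | 10.8% | 7.5% |
| 0.5 | 79.8% | 28.7% | 15.4% |
| 1.0 | about 100% | 79.8% | 46.2% |

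All shifts and SDs are assumptions. The range runs from negligible to decisive, and the documents do not say where the trial falls in it.

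**Does the model remove it?** SAP Section 4 adjusts utilization outcomes for episodes in the 12 months before enrollment. The shift happens after randomization, so that covariate cannot absorb it. The robustness models with fewer controls use the same outcome.

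**When does it arise?** Controls enter FFF at about month 6. From then on both arms have FFF contacts left out, so a 12-month difference comes mainly from the first half. The 90-180 day window lies essentially within the controls' pre-FFF period and gets no such dilution.

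**The case against.** The strongest case for the plan is that use outside the program is a legitimate quantity and substitution is a real effect on it. Food is collected weekly, so counting every FFF attendance would swamp the outcome. The Protocol already promises the wider comparison, FFF encounters are reported separately, and the surveys ask both arms about consultations and classes. Outpatient visits are one secondary count with no row in the power table; Protocol 5.1 and Aim 2 name ED and inpatient use and plan costs instead.

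Much of this stands. It supports keeping the outside-FFF count as a descriptive measure and leaving food pick-ups out of any total. It does not supply the missing analysis: the engagement counts and survey items are not combined with outpatient visits, and the SAP does not schedule the Protocol 5.3 comparison.

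A reader might infer more than the documents support:

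- **That a net reduction is built in.** Only the counting component has a fixed sign. FFF nurses check for eye and foot exams and vaccination (SAP Section 2), which could raise visits outside FFF.
- **That spending falls spuriously.** The exclusion is attached to outpatient visits. Nothing says whether FFF services are billed.
- **That pharmacist and case-management contacts move too.** The documents do not say that controls receive these as usual care.
- **That research lab draws add to the bias.** The treatment arm has an extra draw at month 0 (Protocol 8.4). If draws were counted at all, this would raise the treatment count.

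**Conclusion.** The point holds for dietitian and class contacts. As defined in the SAP, the outpatient count carries a downward counting component in the treatment arm, equal to the mean number of such contacts moved from usual care into FFF. This rests on usual-care contacts being recorded as outpatient encounters, which the documents do not confirm. The size is unknown and may be small, since the SAP itself expects lower take-up among controls. The 5% to 20% range and the false-positive rates are illustrations on assumed inputs. The net treatment difference could have either sign.

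The SAP also needs reconciling with Protocol 5.3 and 8.6. This is a worthwhile, inexpensive correction to one secondary outcome, with a possible extension to paid claims that depends on how FFF services are billed. HbA1c, inpatient and ED outcomes are unaffected.

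**What to change.** In SAP 3.3, for every outpatient window:

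1. Keep the outside-FFF count and label it descriptive.
2. Add count (a): outpatient visits excluding dietitian and diabetes-education contacts in both arms, wherever delivered.
3. Add count (b): the all-source comparison promised in Protocol 5.3, adding FFF dietitian and class contacts, but not food pick-ups, to outpatient visits. State that (b) will rise if FFF increases take-up, as the SAP expects.
4. Leave research lab draws out of all counts in both arms.
5. Base no statement of reduced outpatient use on the outside-FFF count alone.
6. For paid claims, state whether FFF services generate claims. If they do not, apply the same service-type exclusion in both arms.

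The FFF encounter data are already a listed source, so no new FFF data collection is needed. The cost is SAP wording and coding to identify dietitian and education encounters. The outpatient result may look less favourable to the program.

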## Statistical Power and Sample Size Considerations

Using data for current (i.e. self-selected, non-randomized) FFF participants, we conducted parametric power calculations. These take into account the increase in power from controlling for baseline characteristics, but qualitatively similar results were found when we did not include

controls and when we used nonparametric (simulation) methods to estimate power. Similar results were also found when we based the calculations on similar patients in the counties where the two new sites (Lewistown and Scranton) will be located. All power calculations were conducted using STATA Version 15.

The table below shows that with the expected sample size of 500 we will have substantial power to detect small minimal detectable effects (MDE), as well as the ability to conduct heterogeneity analyses for the clinical outcomes. For utilization outcomes, we will have power to detect the (albeit) large reductions in utilization found in the observational literature.

Table 2: Statistical Power to Detect Targeted Minimal Detectable Effects (MDE)

					Required N for
	Mean	Std.Dev.	$\sqrt{1-R^2}$	Target MDE	MDE
Variable					
HbA1c after 180 days	8.58	1.74	0.66	10%	55
HbA1c after 365 days	8.56	1.67	0.66	10%	56
Weight after 180 days	228	64	0.96	10%	228
Weight after 365 days	228	64	0.96	10%	228
Hospital Visit (Inpatient or ED) 0-180 days	0.39	0.49	0.85	30%	397
Hospital Visit (Inpatient or ED) 0-365 days	0.48	0.50	0.87	30%	278
Hospital Visit (Inpatient or ED) 90-365 days	0.40	0.49	0.92	30%	447

We subsequently simulated statistical power for a model that estimates the effects of full engagement. For our primary outcome of HbA1c at 6 months, with power=80% and alpha=0.05 and planned sample size of 500, we can detect:

• Intent to treat effect of assignment to treatment: reduction of 3.7%

• IV treatment effect of full engagement: reduction of 5.2%

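### For hospital payments, the SAP's log model has no rule for the roughly 61% of zeros and can miss or reverse a saving; the 6-month median is almost surely zero in both arms

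*SAP*

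**What the plan says.** SAP 3.3 (6-month outcomes) first lists the binary utilization outcomes: whether a subject was admitted, visited the ED, or did either. It adds visit counts. It then turns to money: "we will test for differences in paid claims both in those categories and in the amount paid among the Geisinger Health Plan beneficiaries". Because large payments are expected, the SAP says, "so we will estimate models in levels, logs, and check for differences in the distribution including the median". The 12-month outcomes text repeats the same set at 12 months.

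Neither document states a rule for zero payments: no added constant, two-part model or log link.

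SAP Table 2 gives the share with any hospital visit, the target reduction and the required sample size. The first such row is "Hospital Visit (Inpatient or ED) 0-180 days 0.39 0.49 0.85 30% 397". The 0-365 day row has a mean of 0.48 and the 90-365 day row 0.40. Section 3.1 of the SAP expects paid claims for more than half of the subjects.

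**The concern.** The log of zero is undefined. Unless something else is specified, a log model of hospital payments runs only on subjects who had a paid hospital visit. The programme is meant to change who has such a visit, so the two groups left in the model are no longer the randomized groups. The coefficient then compares cost per user between differently selected users. It is not the effect of assignment, which is how SAP Section 4 interprets its regression coefficient.

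The median has a different problem. If more than half of each arm has zero payment, both medians are zero and their difference carries no information.

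Cost to the health plan is part of Specific Aim 2 in the protocol. The log and median analyses are the SAP's answer to outliers, so readers will turn to them when the levels result is noisy.

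**Working it through.** **Inputs.** From SAP Table 2: any-visit rates 0.39, 0.48 and 0.40, their SDs and √(1−R²), and the 30% target. Alpha 0.05 and power 80% are stated for the HbA1c simulation ("with power=80% and alpha=0.05 and planned sample size of 500") and assumed, two-sided, for Table 2. Members per arm: 125 as the low end (half of 500, split 1:1) and 250 as the high end. The spread of positive payments is not in the documents; I assume lognormal with log-SD σ from 1.0 to 1.5. I also treat zero hospital payment as equivalent to no visit.

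**1. Is 0.39 the rate the plan used?** Total N = 4(1.960 + 0.842)² × SD²(1−R²) / δ².
- 0-180 days: δ = 0.30 × 0.39 = 0.117; adjusted SD = 0.49 × 0.85 = 0.4165; N = 397.9, against 397 stated.
- 90-365 days: δ = 0.12; adjusted SD = 0.4508; N = 443, against 447.
- 0-365 days: δ = 0.144; adjusted SD = 0.435; N = 286.5, against 278. Rounding of the printed inputs can explain the gap.

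So 0.39 is the reference rate, with a 30% reduction as target.

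**2. Share of zeros** (1 − p at the planning rate; 1 − 0.7p after the target reduction).

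| Window | Control | Treatment |
|---|---|---|
| 0-180 days | 61% | 72.7% |
| 0-365 days | 52% | 66.4% |
| 90-365 days | 60% | 72% |

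Inpatient or ED payments taken separately have at least as many zeros.

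**3. The median.** With 125 per arm the sample median is zero if at most 62 members have a positive payment.
- 0-180 days: P(Bin(125, 0.39) ≤ 62) = 99.4% in control; about 100% in treatment.
- 0-365 days: P(Bin(125, 0.48) ≤ 62) = 67% in control. With 250 per arm it is 72%.

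**4. The log model when avoided visits are unrelated to cost.** About 125 × 0.39 = 49 control and 125 × 0.273 = 34 treated members remain, 83 of 250. The ratio of mean payments over everyone is 0.273/0.39 = 0.70, a 30% saving. The payment distribution among users is the same in both arms, so the true log coefficient is 0. This needs no assumption about the shape of payments. In 2,000 simulated trials (σ = 1.2) the log model found a significant saving in 2.8%, which is chance level.

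**5. The log model when mainly cheaper visits are avoided.** Suppose 50% of below-median-cost and 10% of above-median-cost visits are avoided, 30% in all. The mean log payment is 0.798σ below the centre in the lower half and 0.798σ above it in the upper half. The surviving weights are 0.25 and 0.45, so the coefficient is (0.45 − 0.25) × 0.798σ / 0.70 = 0.228σ. The lower half carries a share Φ(−σ) of total cost, so the true saving is 0.5Φ(−σ) + 0.1[1 − Φ(−σ)].

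| σ | True change in mean | Log model |
|---|---|---|
| 1.0 | −16% | +26% |
| 1.2 | −15% | +31% |
| 1.5 | −13% | +41% |

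At σ = 1.2 the estimate has the wrong sign in 84% of simulated trials with 125 per arm, and in 93% with 250.

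**6. The log model when mainly costlier visits are avoided** (10% of below-median and 50% of above-median). At σ = 1.2 the true change is −45% and the log model shows −24%: right sign, saving understated.

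**The case against.** The best reply has four parts.

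*The SAP never says zeros are dropped.* This is right. A reader might infer a written rule to exclude zero payers; there is none. The SAP is silent, and exclusion is what a plain log does by default. The silence still needs filling, because the obvious patch is not neutral. With an assumed median payment of 5,000 and σ = 1.2, log(1 + payment) on the data of step 4 gives about −1.0 in dollars and −0.22 in thousands of dollars.

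*Total payment may have few zeros.* This is plausible for insured patients with poorly controlled diabetes, though neither document gives the share. A reader might conclude that every log or median cost analysis is unsound. The documents do not support that; the point is limited to hospital categories.

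*Other analyses cover the gap.* The levels model, the any-visit comparison and the visit counts keep everyone, and the distributional check could already extend above the median. This stands and limits the severity. However, the levels test is weak: about 17% power for a 30% saving with 125 per arm and σ = 1.2. The log and median results could therefore carry weight in interpretation.

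*The zero share is uncertain.* The rates come from self-selected programme participants, and claims also capture care outside Geisinger. If 0.39 were the rate under treatment with a 30% effect, the control rate would be 0.39/0.7 = 0.557 and its median would not be zero. Against this, the SAP uses 0.39 as its reference mean and reports similar power results for patients in the counties of the new sites.

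**Conclusion.** The concern holds for inpatient, ED and combined hospital payments. On the SAP's own planning rate, a plain log model at 6 months discards about 61% of controls on the basis of a post-randomization outcome. It shows about 0% against a true 30% saving when avoided visits are unrelated to cost, a result free of distributional assumptions. The reversal, +26% to +41% against −16% to −13%, rests on lognormal payments and on cheaper visits being the ones avoided. A reader might infer that the plan will report a false cost increase; the documents do not say which visits would be avoided, so it can happen but is not predicted.

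The median is uninformative at 6 months if the control rate is near 0.39. Saying it must also be zero at 0-365 days would go too far, since control zeros are only 52% there.

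The matter is worth correcting but does not touch the primary outcome: it affects supplementary specifications of one secondary outcome in the health-plan subset.

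**What to change.** Add to SAP 3.3:

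1. For payment categories with a material share of zeros, replace the log model with a log-link mean model (Poisson or gamma quasi-likelihood, robust standard errors) on all Geisinger Health Plan members, zeros included. It estimates the ratio of mean payments between the randomized arms.
2. If a log model on positive payments is also shown, label it as conditional on use and not as a treatment comparison.
3. Where more than about half of payments are zero, replace the median with a prespecified upper quantile, and add winsorised levels with a stated cut-off. These are needed because the log-link model still targets the mean and does not remove sensitivity to outliers. For 6-month hospital payments the 90th percentile is safer than the 75th: at the target effect only 27.3% of treated members have a positive payment, barely above 25%.
4. Keep the log and median analyses for total amount paid if zeros prove few, and report the share of zeros by arm.

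The cost is SAP wording and a little extra analysis. No new data are needed, and the SAP introduction already allows dated additions.
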